7.0 Rationale and Background

Rationale

This surveillance will be conducted in compliance with the New Drug Re-examination Guideline in Korea and this protocol is written in accordance with the guideline. Safety data of this study will be compared to product label claim for evaluation of the consistency of the safety profile in the real word setting.

Background

Approximately 25% of IBD patients are diagnosed as children, and the IBD characteristics of pediatric patients differ from those of adults as outlined below.¹⁻³ A recent single center study showed that the incidence of pediatric IBD has been rapidly increasing in Korea in recent years.⁴ In this study, relevant family history was less prevalent and phenotypic expression differed from what was seen in Western countries.

Children with Crohn's disease can experience abdominal pain, intestinal obstruction and strictures, fistulas, abscesses, perianal disease, adverse events of treatment such as corticosteroids and surgery, and nutritional complications. A major difference between adult and pediatric CD is an impact of malnutrition. It can lead to delayed puberty and growth impairment which result in significant psychosocial complications.⁵⁻⁸ At first, the goal of treatment of CD for children is to induce and maintain clinical remission. Restoration and/or preservation of normal growth and pubertal development are additional therapeutic goals in children with CD.⁹

The first line conventional therapy for mild patients includes 5-aminosalicylates and exclusive enteral nutrition (EEN). Corticosteroids are prescribed for moderate patients for induction. Immunomodulators such as azathioprine, 6-MP or MTX are used for maintenance for those.¹⁰

Therapeutic options for Crohn's disease are evolving, and recently, a new treatment approach has been suggested using biological agents to heal mucosa and alter natural history of disease.¹¹⁻¹²

Until now, TNF blockade including adalimumab and infliximab has been prescribed for adult CD patients. In randomized controlled trials, adalimumab rapidly induced and

maintained clinical remission in adults.¹³⁻¹⁷ The efficacy and safety of adalimumab for induction and maintenance of clinical remission in Western children with moderate to severe CD who had failed corticosteroids or immunosuppressants, including prior infliximab in > 40% of subjects, was demonstrated in the Imagine 1 trial.

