9.3 Variables

Demographics

Basic demographics including patient initials, age (year and month of birth), sex, weight, height, name of institution, department and physician will be taken and recorded.

Diagnosis and Medical History

Diagnosis and medical history including previous TB history or vaccination, will be taken and recorded and will include the following items to get patient's medical status:

- CD related history ; date of pediatric CD diagnosis, involved intestinal area, presence of draining fistula, previous CD related therapy including antibiotics, steroids, 5-ASA, Immunosuppressants, biologics and nutritional therapy
- Previous TB history ; presence of TB, TB treatment regimen received, completeness and appropriateness of the therapy regimen, vaccination
- Other medical history ; history of previous disease(s), concurrent disease(s), history of allergy, pregnancy etc.

PPD Skin Test

PPD skin test will be performed and recorded. It will include: Date of PPD test, induration at PPD test site (in mm). (Refer to MFDS Guideline for Latent TB Management in TNF-Antagonist Use and TB screening Aide provided by AbbVie.)

Chest X-ray

Chest X-ray interpretation result will be taken and recorded and will include: Date of Chest-X-Ray, presence of latent or active TB lesion. (Refer to MFDS Guideline for Latent TB Management in TNF-Antagonist Use and TB screening Aide provided by AbbVie.)

Interferon gamma release assay

Interferon gamma release assay will be performed, recorded and will include: date of interferon gamma release assay and result. (Refer to MFDS Guideline for Latent TB Management in TNF-Antagonist Use and TB screening Aide provided by AbbVie.)

Treatment with Humira®

Patients will be administered Humira® as per the package label. Unit dose, frequency, length of treatment (start date, end date) will be recorded on the appropriate case report form.

Concomitant Medication

Concomitant medications, including TB prophylaxis regimen, corticosteroids, immunosuppressants, will be recorded and will include: generic name (brand name in case of combination drug), total daily dose, length of administration (start date and end date), indication(s).

Safety (Adverse Event)

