For induction effectiveness of Humira®, the effectiveness analysis data set will include all subjects who have been administered Humira® and prescribed Humira® for 4 weeks including induction period (± 1 week) and for whom effectiveness evaluation parameters have been recorded. And for maintenance effectiveness of Humira®, effectiveness analysis data set will include all subjects who have been administered Humira® and prescribed Humira® for 6 months (± 4 weeks) and for whom effectiveness evaluation parameters have been recorded. The subjects whose effectiveness evaluation was not properly conducted because their data from evaluation parameters were missing or they discontinued administration prior to the effectiveness evaluation will be excluded from the evaluation.

Safety Analysis

The adverse events will be coded by MedDRA dictionary. The number and percentage of subjects reporting any serious adverse events/adverse drug reactions will be tabulated overall and by MedDRA 17.0 or more recent version, in preferred term. The number and percentage of subjects reporting unexpected (unlabeled) adverse drug reactions will be tabulated in a similar fashion.

To investigate the factors affecting the safety, the number and percentage of subjects reporting adverse events will also be classified by various background factors (e.g., demographic factors, treatment factors such as medical history, dosing and administration, concomitant medications, beginning of administration before/after the registration date, etc.) and tabulated. If the incidence of adverse events in the subjects who began the administration before/after the registration date has statistical significance, it will be presented as a separate item. In addition, if there are patients who have already been

administered Humira® when participating in the surveillance, their adverse events from the first administration of Humira® to the inclusion will be presented in a separate table. If data from special patient groups are collected, they will be extracted and tabulated separately for adverse events/adverse drug reactions.

Effectiveness Analysis

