The effectiveness assessment of Humira® induction therapy and maintenance therapy will be presented by the number and percentage of the subjects with clinical response. Clinical response is defined as decrease in PCDAI score from baseline by ≥ 15 points and if CDAI score is collected, Clinical response is defined as decrease in CDAI score from baseline by ≥ 70 points.

To investigate the factors affecting the effectiveness, the number and percentage of subjects with clinical response will also be classified by background factors (e.g., demographic factors, treatment factors such as medical history, dosing and administration, concomitant medications, beginning of administration before/after the registration date, etc.) and tabulated. If the effectiveness evaluation of above factors has statistical significance, it will be presented as a separate item.

Statistical Methods

The descriptive statistics for safety and effectiveness parameter in each year will be presented in annual reports.

In final report (Re-examination report), safety and effectiveness outcome by background factor will be summarized and analyzed. The analysis for categorical variables will be performed using chi-square test or fisher's exact test and continuous variables will be performed using Wilcoxon rank sum test or t-test. Also, incidence rate of adverse event collected in overall PMS period will be analyzed and 95% CI will be presented.

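### The response rate in section 9.7 can include the effect of Crohn's disease treatment added after the first Humira dose, and no planned analysis isolates it

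*Combined protocol and SAP*

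**What the plan says.** **Definition.** Section 9.7 states: "Clinical response is defined as decrease in PCDAI score from baseline by ≥ 15 points". Where CDAI is available, "Clinical response is defined as decrease in CDAI score from baseline by ≥ 70 points". Neither rule has a condition on other treatment.

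**What is reported.** "The effectiveness assessment of Humira® induction therapy and maintenance therapy will be presented by the number and percentage of the subjects with clinical response". The percentage is thus presented as the result of Humira.

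**Who is left out.** Under Analysis Population in 9.7, subjects leave the effectiveness set if evaluation data are missing or if "they discontinued administration prior to the effectiveness evaluation will be excluded from the evaluation". Adding or increasing another Crohn's treatment is not a reason for exclusion.

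**What is collected.** Section 9.3: "Concomitant medications, including TB prophylaxis regimen, corticosteroids, immunosuppressants, will be recorded". The listed items are drug name, total daily dose, start and end dates, and indication.

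**How it is used.** For effectiveness, section 9.7 uses concomitant medication only as one of several background factors by which response is tabulated and tested. A factor is presented separately if it is statistically significant.

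**Limitations.** Section 9.9 names open-label, non-randomised data and reporting bias. It does not mention added treatment.

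**The concern.** The drugs that may be added act on the same score. Section 7.0 says of conventional therapy: "Corticosteroids are prescribed for moderate patients for induction", and it describes immunomodulators as maintenance treatment. The design in 9.1 and the criteria in 9.2 do not restrict concomitant therapy, and there is no comparison group in which the same additions would occur. Suppose a child does poorly on Humira, is given a corticosteroid between the first dose and the assessment, and then falls by 15 points. That child is counted in the same way as one who improved with nothing added.

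Section 8.0 hypothesises that Humira will be efficacious in Korean children, and the responder percentage is the only effectiveness outcome planned. A reader of the re-examination report could not tell how much of that percentage came from children whose treatment had been stepped up.

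**Working it through.** **The plan's own figures.** The plan gives no expected response rate and no share of subjects with added therapy, so there is no effectiveness figure to reproduce. The one probability in 9.7 concerns safety: 1 − e^(−600 × 0.005) = 1 − e^(−3) = 0.9502. It reproduces and has no bearing here.

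**Step 1: does any rule deal with added therapy?** The response definition has no such condition. The exclusions cover only missing evaluation data and stopping Humira. The breakdown by concomitant medication does not distinguish therapy present at baseline from therapy started or increased later, and it leaves responder status unchanged. Section 9.9 is silent. So no rule exists.

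**Step 2: how far can the rate move?** Let
- f = share of evaluable subjects with Crohn's therapy added or increased before the assessment,
- q = their response rate under the definition as written,
- r = response rate in all other evaluable subjects.

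Rate as written = (1 − f)r + fq.

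Rate counting the f group as non-responders = (1 − f)r.

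Difference = f × q, whatever r is.

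The documents give none of the three quantities. With assumed values and r = 60%:

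| f (assumed) | q (assumed) | As written | Non-responder counting | Difference |
|---|---|---|---|---|
| 5% | 50% | 59.5% | 57.0% | 2.5 points |
| 10% | 70% | 61.0% | 54.0% | 7.0 points |
| 20% | 70% | 62.0% | 48.0% | 14.0 points |
| 30% | 90% | 69.0% | 42.0% | 27.0 points |

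The spread of 2.5 to 27 points shows that the answer depends wholly on the assumed inputs. It is not an estimate. The difference f × q is also the most that this rule could change the rate, because some of these subjects may have responded to Humira alone.

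**Step 3: would the planned breakdown reveal it?** Even if the table did split subjects by added therapy, it compares q with r. Take f = 20% and q = r = 60%. The table shows no difference and the test gives no reason for separate presentation. Yet the rate as written is 60%, and the rate with non-responder counting is 0.80 × 60% = 48%, a gap of 12 points. If added therapy restores response to the level of the other subjects, the comparison hides the issue.

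**Step 4: can the collected data support a sensitivity rate?** Name, total daily dose, dates and indication allow most starts of a drug for Crohn's disease to be placed before or after the first Humira dose. There are three limits:
- Section 9.3 does not say that a dose change is recorded as a separate entry, so increases may be missed.
- Nutritional therapy appears there only as previous therapy.
- Table 2 in 9.5 expects 29 + 10 = 39 of about 141 subjects (39/141 = 28%) to have started Humira before enrolment, so their early medication records may be retrospective.

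**The case against.** **Routine-practice response is a legitimate target.** This is non-interventional surveillance with mainly safety objectives; effectiveness sits under other information in section 8.0. Response on Humira with whatever else is prescribed is a defensible quantity. This stands, and it is why the current rate should stay. But the plan does not state that choice, and it labels the result as Humira induction and maintenance effectiveness.

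**The label population may respond less to added conventional drugs.** Section 9.5 describes the indication as severely active disease after inadequate response to, intolerance of, or contraindication to primary nutritional therapy, corticosteroids and/or immunomodulators. Many enrolled children will have failed, or be unable to take, at least one of these. This stands against assuming a high response to added therapy. It does not remove the issue, since the and/or allows failure of only one class.

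**The direction of the net bias is not established.** A reader might infer that the rate can only be too high. The documents do not support that. The definition equally ignores reduction or withdrawal of corticosteroids that were ongoing at baseline, which could raise the score and lower apparent response.

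**Non-responder counting overcorrects.** It also fails children who would have responded anyway, for example where an immunosuppressant was started as planned combination therapy. This stands: the result is a lower bound, not a corrected rate. It should be limited to therapy given for Crohn's disease, so that a steroid course for another condition does not count as failure.

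**Part is already handled.** Most switches to another biologic would leave the effectiveness set through the discontinuation rule. This is fair, and it makes that component small.

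**Conclusion.** The point holds as a cheap improvement. The rate in 9.7 counts every sufficient fall in score as response to Humira, including falls after other Crohn's treatment was started or increased, and the planned breakdown does not isolate those subjects.

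The size is unknown. With f and q unstated, a reader might assume, say, that 10% to 20% of subjects are non-responders to Humira who receive added therapy, and that 40% to 70% of them respond to it. That gives an overstatement of 0.10 × 0.40 = 4 to 0.20 × 0.70 = 14 points. The documents supply neither input, and the label population in 9.5 makes the second doubtful, so no such figure should be relied on.

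A reader might also infer from section 7.0, which lists adverse events of corticosteroids among the burdens of the disease, that the plan ought to show corticosteroid-free response. That is not an aim stated anywhere in the plan.

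What can be said is limited. With respect to added therapy only, and assuming that added therapy does not turn a responder into a non-responder, response to Humira alone lies between the non-responder rate and the rate as written. Neither end accounts for tapering of baseline corticosteroids.

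**What to change.** In section 9.7, Effectiveness Analysis:

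1. Keep the current rate and describe it as response on Humira as used in routine practice.
2. At week 4 and month 6, report the number and percentage of evaluable subjects who, between the first Humira dose and the assessment, started or increased a corticosteroid or immunosuppressant, or started another biologic, with Crohn's disease as the recorded indication.
3. At both times, add a sensitivity response rate that counts those subjects as non-responders, with a 95% CI, labelled as a lower bound with respect to added therapy. Section 9.7 now plans a CI only for adverse event incidence.
4. Derive both from the drug name, total daily dose, dates and indication in 9.3. State the limits: increases are visible only if dose changes are separate entries, nutritional therapy started later may not be captured, and records for the roughly 39 of 141 subjects who began Humira before enrolment may be retrospective.

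Corticosteroid-free response at month 6 may be shown as an optional descriptive figure.

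The cost is wording and programming, with no new visit. The downside is that the sensitivity rate will be no higher than the current one, usually lower, and may understate Humira's effect. Nothing here changes how children are treated.

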9.2 Setting

Selection of Study Population

Pediatric CD patients who has been prescribed Humira® by the treating physician as per Korean label will be enrolled.

The patients who are receiving Humira® for pediatric CD during study period and meet the inclusion /exclusion criteria will be enrolled in the sites which signed a contract with AbbVie.

Once the study agreement is in place, the surveillance will be initiated at the site, and all patients who are prescribed Humira® for pediatric CD treatment during the surveillance period and who meet the inclusion /exclusion criteria will be enrolled in the study until the assigned number of subjects are registered at the site.

Inclusion Criteria

1. Pediatric patients with Crohn's Disease who are prescribed Humira in accordance with the Korean label for Humira authorization (labeling)
2. Patients who have given written authorization or patients whose legal representatives have given it to use their personal health data for the purposes of this study.

Physician will refer to the product market authorization (label) for inclusion criteria.

Exclusion Criteria

Patient with any of the following should not be registered in this surveillance:

1. Any contraindications to Humira as listed on the approved product market authorization (labeling)
2. Patients who is participating on other clinical trials.

Patients will be observed for 6 months following first dose of Humira®.

It is planned to include all patients who are treated with Humira® until the planned number of cases are collected to obtain meaningful safety data including TB incidence in the early stage of the study conduct. Once this study has been initiated in an institution, physicians are recommended to include/recruit all eligible patients who are prescribed Humira®.

An evaluable patient is a patient who has been administered Humira® at least once and has safety information at subsequent visits. (or telephone contact, correspondence)

Drop-out patients also will be considered for safety evaluation, if the safety information is obtained by follow-up contact. If there is loss of follow-up, the reason will be recorded.

Investigator Selection Criteria

The surveillance will be conducted in medical institutions in Korea. The institutions include clinics and hospitals. The physician must meet the following criteria:

1. A physician who is working in a hospital or clinic and has a patient pool eligible for this surveillance.

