9.5 Study Size**Number of Patients to be enrolled**

At least 600 subjects were to be collected for surveillance to meet the local regulatory requirements, but the number of subjects was adjusted to 141 subjects based on the followings:

1) Significantly low incidence and prevalence of Pediatric CD

Based on the data obtained from 1996 to 2002 in North America, 93.6 per 100,000 people suffered from Crohn's disease and the incidence rate of Crohn's disease in children aged less than 18 years was 3.0 per 100,000 people.¹⁸ Additionally, it is reported that when considering the ethnic differences, Crohn's disease is more prevalent in developed countries and relatively less common in Asia;¹⁹ for example, a retrospective study conducted in China revealed that the prevalence of Crohn's disease was estimated to be 1.4 per 100,000 people,²⁰ which was much less than that reported in North America.

According to the data reported to Korea Health Insurance Review & Assessment Service in 2015, the number of patients aged 19 years or younger who are with 'K50: Crohn's disease [regional enteritis]' was only 3,051. Considering that ages eligible for enrollment in this Post-Marketing Surveillance are between 6 years and 17 years according to its approved label in Korea, it is expected that the number of patients eligible for this Post-Marketing Surveillance would be much less than the number aforementioned, but there is no specific domestic data to prove it in Korea.

2) Humira is not a primary therapeutic agent for Pediatric CD

Humira® is indicated only to patients with severely active Crohn's disease with inadequate response, intolerance, or contraindication to primary trophotherapy, corticosteroids and/or immunomodulators according to the approved label, which is reflected in the very limited number of patients with Crohn's disease of all ages who received treatment with biologics, based on the data reported to Korea Health Insurance Review & Assessment Service [Table 1].

[Table 1] The estimated number of patients diagnosed with Crohn's disease and proportion of those patients with anti-TNF agents prescription

	The number of patients diagnosed*	Patients prescribed with anti-TNF agents	
		The mean number of patients†	% ‡
All ages	17,651	1,684	9.5%

* The number of patients diagnosed: The number of patients diagnosed in 2015 according to the disease code (K50: Crohn's disease [regional enteritis]); source: Health Insurance Review & Assessment Service; unit: people

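### Response is an absolute fall of 15 PCDAI (70 CDAI) points with no minimum baseline, so the plan should say how children who start too low to respond are shown

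*Combined protocol and SAP*

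**What the plan says.** **Endpoint.** In the combined protocol and SAP, Section 9.7 (Effectiveness Analysis) gives one effectiveness outcome, used for both induction and maintenance: "Clinical response is defined as decrease in PCDAI score from baseline by ≥ 15 points". For CDAI, where available: "Clinical response is defined as decrease in CDAI score from baseline by ≥ 70 points". No remission, relative-change or mean-change measure is planned beside it.

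**Effectiveness sets.** Section 9.7 (Analysis Population) takes subjects treated for the period "for whom effectiveness evaluation parameters have been recorded". The stated reasons for leaving a subject out are that "their data from evaluation parameters were missing or they discontinued administration prior to the effectiveness evaluation will be excluded from the evaluation". A low starting score is not among them.

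**Entry.** Section 9.2 admits patients "who are prescribed Humira in accordance with the Korean label", with no PCDAI or CDAI cut-off. Section 9.5 says that Humira "is indicated only to patients with severely active" disease with "inadequate response, intolerance, or contraindication to primary trophotherapy, corticosteroids and/or immunomodulators". Section 7.0 calls the population moderate to severe. Neither description carries a score.

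**Baseline.** Section 9.3 (Effectiveness) asks for a score from before Humira treatment. It gives visit windows for week 4 and month 6 but none for the baseline.

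**Factor tests.** Section 9.7 tabulates response by background factors, including medical history, concomitant medication and whether Humira was started before or after registration. It uses chi-square or Fisher's exact tests, and significant factors are reported as a separate item. No adjustment for baseline score is mentioned.

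**The concern.** An absolute-fall endpoint can be met only by a subject who starts high enough to fall that far. A child recorded at PCDAI 12.5 who later scores 0 has done as well as the scale allows, yet counts as a treatment failure.

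Two results are exposed. The first is the response percentage, which is the only planned evidence on effectiveness. Each such child adds to the denominator and can never add to the numerator. The second is the set of factor tests. If one level of a factor holds more low starters than another, response will look worse there for arithmetic reasons, and Section 9.7 would then list that factor as one that affects effectiveness.

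**Working it through.** **The plan's own figures.** The documents give no response rate, baseline distribution or effectiveness power. The only probability calculation is for safety: 1 - exp(-600 x 0.005) = 1 - exp(-3) = 0.9502. It reproduces but has no bearing here.

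**Inputs from the documents.** Threshold 15 PCDAI or 70 CDAI points (9.7). About 141 subjects (9.5). By Table 2 in 9.5, 71 + 31 = 102 start Humira after enrolment and 29 + 10 = 39 start before it (39/141 = 27.7%).

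**Assumptions.** Scores cannot go below 0. A fraction f of subjects starts below the threshold. The others respond at rate p. All 141 are evaluable. Tests are two-sided at 0.05, a level the plan does not state.

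**Step 1: the response rate.** The rate is f x 0 + (1 - f) x p = (1 - f) x p, so the shortfall is f x p. At p = 80%:

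| f | Children of 141 | Reported rate | Shortfall (points) |
|---|---|---|---|
| 2% | about 3 | 78.4% | 1.6 |
| 5% | about 7 | 76% | 4 |
| 10% | about 14 | 72% | 8 |

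For scale, the standard error of an 80% rate in 141 subjects is sqrt(0.8 x 0.2 / 141) = 3.4 points. At f = 2% the shortfall is about half of that; at f = 10% it is more than twice that.

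**Step 2: the factor tests.** Take the factor that Section 9.7 names and Section 9.5 sizes: start after versus before enrolment, 102 versus 39. Give both groups the same p, so that any significant result is false. Exact enumeration of the two binomials gives these rejection rates:

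| f in the 102 | f in the 39 | Chi-square, p = 70% | Fisher, p = 70% | Chi-square, p = 80% | Fisher, p = 80% |
|---|---|---|---|---|---|
| 0% | 0% | 0.051 | 0.039 | 0.051 | 0.035 |
| 10% | 10% | 0.051 | 0.037 | 0.050 | 0.037 |
| 5% | 10% | 0.073 | 0.055 | 0.085 | 0.061 |
| 5% | 20% | 0.223 | 0.179 | 0.309 | 0.256 |

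An even spread of low baselines leaves the false-positive rate nominal. A mild imbalance raises it slightly, and only a marked imbalance raises it a lot.

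**Step 3: just above the threshold.** A child at PCDAI 15 must reach 0 to respond, and one at 17.5 must reach 2.5 or less. Dropping children below 15 removes the impossible cases, but response still depends on baseline among the rest.

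**The case against.** The strongest reply is that such children should hardly exist. The label as described in 9.5 requires severely active disease, and intolerance is a condition added to that, not a way in for children with little activity. A reader might infer from the word intolerance alone that mildly active children are admitted; the full sentence does not support that. A reader might also infer that earlier corticosteroids or enteral nutrition lower the recorded baseline. The documents list these as prior treatments but say nothing about their effect on the score.

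This stands, and it keeps the expected f small. It does not make f zero. No score is checked at entry, and with no baseline window the recorded score need not reflect activity when Humira was prescribed.

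The second reply is that (1 - f) x p is the correct value of the stated endpoint in the stated population. That also stands: counting all subjects is defensible and should remain. The plan gives the reader no way to see how much of the non-response is built in.

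The third reply is that effectiveness here is secondary and descriptive. Section 8.0 frames the objective as safety, and there is no effectiveness threshold or power. This bears on severity and is accepted.

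**Conclusion.** The point holds as a minor one. By the stated rule, a child whose baseline is below 15 PCDAI (70 CDAI) points stays in the denominator and cannot respond, provided that scores cannot go below 0, which the documents do not state.

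These children can lower the reported rate from p to (1 - f) x p: by 1.6 to 8 points for f from 2% to 10% at an assumed p of 80%. Both p and f are assumptions, and the label wording favours the low end.

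A reader might infer that the response rate and the factor tests are in fact distorted. The documents do not support that. They give no baseline distribution, and the factor tests go wrong only if low baselines fall unevenly across the levels of a factor.

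**What to change.** In Section 9.7, Effectiveness Analysis, fix the following before the analysis:

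- Keep the all-subject response percentage as planned.
- Report the distribution of baseline PCDAI, and of CDAI where collected, with the number of subjects below 15 (70).
- Beside the all-subject figure, show the response percentage among subjects with baseline PCDAI of at least 15 (for the CDAI table, at least 70). List the visit scores of those below.
- Repeat the factor tests on response in that restricted set, adjusted for or stratified by baseline score. The restriction alone is not enough, because response still depends on baseline just above the threshold.

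The cost is a short addition to 9.7, one extra row per table and a repeat of the factor tests, all from scores already collected. The restricted figures have a slightly smaller denominator. If no child starts below the threshold, the two percentages coincide.

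### Section 9.7 singles out a background factor only when an unadjusted test is significant, and plans no effect estimate or interval for any factor

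*Combined protocol and SAP*

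**What the plan says.** All of the relevant text is in section 9.7, Data Analysis.

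- **Effectiveness.** Clinical response is counted by background factor, the factors being given as examples: "demographic factors, treatment factors such as medical history, dosing and administration, concomitant medications, beginning of administration before/after the registration date, etc". The trigger follows: "If the effectiveness evaluation of above factors has statistical significance, it will be presented as a separate item". It applies to all of the factors.
- **Outcomes under that trigger.** There are two, induction and maintenance response: "The effectiveness assessment of Humira® induction therapy and maintenance therapy will be presented by the number and percentage of the subjects with clinical response". A second definition may add to them: "if CDAI score is collected, Clinical response is defined as decrease in CDAI score from baseline by ≥ 70 points".
- **Safety.** Adverse events are counted by a similar list of factors. The trigger here covers one factor only: "If the incidence of adverse events in the subjects who began the administration before/after the registration date has statistical significance". Events that occurred before inclusion in children already on treatment get their own table, with no significance condition.
- **Statistical methods.** "In final report (Re-examination report), safety and effectiveness outcome by background factor will be summarized and analyzed". The tests are chi-square or Fisher for categorical variables and Wilcoxon or t-test for continuous ones. The only interval named is a 95% CI for the incidence of adverse events.

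The section gives no significance level, closed factor list, multiplicity rule or exploratory label, and no difference, ratio or interval for any factor. Section 9.9, on limitations, does not mention the matter.

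**The concern.** The stated purpose of these tables is to find factors that affect safety and effectiveness, and the separate items are what a reader of the re-examination report will take from them. Under the rule, a p-value alone decides which factors receive that prominence, and this has three consequences.

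1. Many single-factor tests at an unadjusted level produce some chance separate items.
2. A factor selected because it crossed a significance threshold in a small sample tends to show too large an effect, and no interval is planned that would reveal the imprecision.
3. The comparison of children who started before and after registration bears on the reporting bias with historical safety data that section 9.9 concedes. If it gets no separate item because the test was not significant, a reader may take that as reassurance, although the test has little power for a moderate gap.

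**Working it through.** The documents give no error rate, number of tests or power for the factor analyses, so there is no figure of the plan's own to reproduce.

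**Inputs from the documents**
- Two response outcomes under the effectiveness trigger, and one factor under the safety trigger (section 9.7).
- 141 subjects (section 9.5).
- Table 2 in section 9.5: treatment started after enrolment in 71 + 31 = 102, and before enrolment in 29 + 10 = 39.

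**Assumptions**
- Two-sided 5% level and independent tests.
- Number of factors: 10 to 29, with 24 as a working value. The plan states no number. Section 9.3 collects enough items for such a count, for example "presence of draining fistula, previous CD related therapy including antibiotics, steroids, 5-ASA, Immunosuppressants, biologics and nutritional therapy".
- All response and adverse event rates below are illustrative.

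**Step 1. False separate items if no factor matters.** For m tests at level a, the expected number is m × a and the chance of at least one is 1 − (1 − a)^m.

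| Factors and outcomes | m | Expected, a = 0.05 | At least one, a = 0.05 | At least one, a = 0.03 |
|---|---|---|---|---|
| 10 × 2 | 20 | 1.0 | 1 − 0.95^20 = 64% | 1 − 0.97^20 = 46% |
| 24 × 2 + 1 | 49 | 2.45 | 1 − 0.95^49 = 92% | 1 − 0.97^49 = 78% |
| 29 × 2 | 58 | 2.9 | 1 − 0.95^58 = 95% | 1 − 0.97^58 = 83% |

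The last column allows for Fisher's test, whose true level in simulations with 141 subjects was about 0.025 to 0.04. At 0.03 the expected numbers fall to 0.6, 1.47 and 1.74. Correlation between factors or outcomes lowers the chance of at least one false item but leaves the expected number unchanged.

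**Step 2. Overstatement after selection.** Response in 71 v 70 subjects, chi-square test without continuity correction, average observed difference among the significant results:
- 80% v 70%: power 28%; the true 10 points appear as about 19.
- 80% v 60%: power about 75%; the true 20 points appear as about 23.

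Uneven splits are worse. For 80% v 70%, the 10 points appear as about 20 with a 70:30 split and about 29 with a 90:10 split. The effectiveness sets exclude subjects with missing evaluations or early discontinuation, so they will be smaller than 141 and power will be lower.

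**Step 3. Power of the safety trigger, 102 v 39 subjects, same test**
- 45% v 35%: 18%.
- 50% v 30%: 58%.
- 40% v 20%: 63%.

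The first rate belongs to the group of 102. With the two rates exchanged, the figures are 20%, 61% and 68%. A real 10-point gap would therefore miss the trigger about four times in five.

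**Step 4. Share of separate items that are false.** If k of m tests have a true association and are tested with power w, the share is 0.05(m − k) / [0.05(m − k) + k × w]. With m = 48:
- k = 0: 100%.
- k = 4, w = 0.3: 2.2 / (2.2 + 1.2) = 65%.
- k = 8, w = 0.3: 2.0 / (2.0 + 2.4) = 45%.
- k = 8, w = 0.8: 2.0 / (2.0 + 6.4) = 24%.

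**The case against.** The best defence is that nothing is hidden. Both analyses tabulate every factor unconditionally. Start before or after registration is itself a listed factor, and events before inclusion have their own table. This is single-arm surveillance with a descriptive safety objective, no decision rule depends on the factor tables, and section 9.9 admits that the patients are not randomized. All of that stands. A reader might infer that non-significant factors go unreported; the text does not support this, because the trigger adds emphasis and removes no result.

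The count of tests can also be overstated. A reader might take the trigger to cover adverse events across all factors as well, which with 24 factors gives 24 × 3 = 72 tests, 3.6 expected false items and a 97.5% chance of at least one. Three outcomes are indeed analysed by factor in the final report ("safety and effectiveness outcome by background factor will be summarized and analyzed"), but for safety the separate item depends on significance for one factor only. With 24 factors the triggers cover 49 tests. The 24 is itself an assumption, and some collected items may be too sparse ever to reach significance.

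What the defence does not answer is that emphasis is the purpose of a separate item, and that the tables behind it hold only counts and percentages. A reader has no interval against which to judge either a highlighted factor or one left in the table.

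**Conclusion.** The point holds as a weakness in how factor results are selected for emphasis. It is worth correcting before the final report, but it does not touch the main safety summary. At an assumed 5% level with independent tests and no true effects, the two triggers yield about 1 to 3 false separate items for 10 to 29 factors, and the chance of at least one is 64% to 95%. Conservative Fisher tests bring the chance down to 46% for 10 factors and 78% for 24. The overstatement is nearly twofold for a true 10-point response difference in equal groups and modest for 20 points. The safety trigger has about 18% power for 45% v 35% and about 60% for a 20-point gap, so a non-significant result there is not reassurance.

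It is tempting to conclude that the highlighted factors will mostly be chance findings. The documents do not support that. The false share depends on how many factors truly matter and on the power for each, neither of which is documented, and step 4 runs from 24% to 100%.

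**What to change.** In section 9.7:

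1. Delete both significance triggers.
2. In the final report, give the difference in proportions (or odds ratio) with a 95% CI for every tabulated factor, including start before or after registration, whether significant or not.
3. Label the factor analyses exploratory and state the number of tests carried out.

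A multiplicity adjustment, such as Holm or false discovery rate within each outcome, is optional. It is needed only if a factor is to be called significant.

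The cost is revised wording and a few more table columns. No new data are needed and no planned table is lost. The downside is that fewer factors will be singled out.
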